6. DOSING DELAYS/DOSE MODIFICATIONS

6.1 General AE Management and Dose Modification Guidelines

There will be no dose reduction for atezolizumab in this study.

Patients may temporarily suspend study treatment for up to 84 days (12 weeks) beyond the scheduled date of delayed infusion if study drug-related toxicity requiring dose suspension is experienced. If atezolizumab is held because of AEs for >84 days beyond the scheduled date of infusion, the patient will be discontinued from atezolizumab and will be followed for safety and efficacy as specified in this protocol. If the AE resolves within 84 days and the patient is receiving corticosteroid therapy for the event, atezolizumab may be held for longer than 84 days (up to 4 weeks) in order to allow tapering of the steroid dose to ≤ 10 mg oral prednisone or equivalent.

Dose interruptions for reasons other than toxicity, such as surgical procedures, may be allowed. The acceptable length of interruption will be at the discretion of the study PI in consultation with CTEP.

The primary approach to grade 1 to 2 irAEs is supportive and symptomatic care with continued treatment with atezolizumab; for higher-grade irAEs, atezolizumab should be withheld and oral and/or parenteral steroids administered. Recurrent grade 2 irAEs may also mandate withholding atezolizumab or the use of steroids. Assessment of the benefit risk balance should be made by the investigator, with consideration of the totality of information as it pertains to the nature of the toxicity and the degree of clinical benefit a given patient may be experiencing prior to further administration of atezolizumab. Atezolizumab should be permanently discontinued in patients with life threatening irAEs.

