Pulmonary event, Grade 1	
 Continue atezolizumab and monitor closely. Re-evaluate on serial imaging. Consider patient referral to pulmonary specialist.
Pulmonary event, Grade 2	
 Withhold atezolizumab for up to 12 weeks after event onset.^a

Event	Management
	
 ● Refer patient to pulmonary and infectious disease specialists and consider bronchoscopy or BAL. ● Initiate treatment with corticosteroids equivalent to 1–2 mg/kg/day oral prednisone. ● If event resolves to Grade 1 or better, resume atezolizumab.^b ● If event does not resolve to Grade 1 or better while withholding atezolizumab, permanently discontinue atezolizumab. ● For recurrent events, treat as a Grade 3 or 4 event.
Pulmonary event, Grade 3 or 4	
 ● Permanently discontinue atezolizumab. ● Bronchoscopy or BAL is recommended. ● Initiate treatment with corticosteroids equivalent to 1–2 mg/kg/day oral prednisone. ● If event does not improve within 48 hours after initiating corticosteroids, consider adding an immunosuppressive agent. ● If event resolves to Grade 1 or better, taper corticosteroids over ≥1 month.

BAL = bronchoscopic alveolar lavage

^a Atezolizumab may be withheld for a longer period of time (*i.e.*, >12 weeks after event onset) to allow for corticosteroids (if initiated) to be reduced to the equivalent of ≤10 mg/day oral prednisone. The acceptable length of the extended period of time must be determined by the investigator and the Medical Monitor.

^b If corticosteroids have been initiated, they must be tapered over ≥1 month to the equivalent of ≤10 mg/day oral prednisone before atezolizumab can be resumed.

Hepatic events

Immune-mediated hepatitis has been associated with the administration of atezolizumab. Eligible patients must have adequate liver function, as manifested by measurements of total bilirubin and hepatic transaminases, and liver function will be monitored throughout study treatment. Management guidelines for hepatic events are provided in the table below.

Patients with right upper-quadrant abdominal pain and/or unexplained nausea or vomiting should have liver function tests (LFTs) performed immediately and reviewed before administration of the next dose of study drug.

For patients with elevated LFTs, concurrent medication, viral hepatitis, and toxic or neoplastic etiologies should be considered and addressed, as appropriate.

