Thyroid disorders, adrenal insufficiency, diabetes mellitus, and pituitary disorders have been associated with the administration of atezolizumab. Management guidelines for endocrine events are provided in the table below.

Patients experiencing one or more unexplained AEs possibly indicative of endocrine dysfunction (including headache, fatigue, myalgias, impotence, mental status changes, and constipation) should be investigated for the presence of thyroid, pituitary, or adrenal endocrinopathies. The patient should be referred to an endocrinologist if an endocrinopathy is suspected. Thyroid

stimulating hormone (TSH) and free T3 and T4 levels should be measured to determine whether thyroid abnormalities are present. Pituitary hormone levels and function tests [e.g., TSH, growth hormone, luteinizing hormone, follicle-stimulating hormone, testosterone, prolactin, adrenocorticotrophic hormone (ACTH) levels, and ACTH stimulation test] and MRI of the brain (with detailed pituitary sections) may help to differentiate primary pituitary insufficiency from primary adrenal insufficiency. The table below describes dose management guidelines for hyperthyroidism, hypothyroidism, symptomatic adrenal insufficiency, and hyperglycemia.

Event	Management
Asymptomatic hypothyroidism	
 • Continue atezolizumab. • Initiate treatment with thyroid replacement hormone. • Monitor TSH weekly.
Symptomatic hypothyroidism	
 • Withhold atezolizumab. • Initiate treatment with thyroid replacement hormone. • Monitor TSH weekly. • Consider patient referral to endocrinologist. • Resume atezolizumab when symptoms are controlled and thyroid function is improving.
Asymptomatic hyperthyroidism	
TSH ≥ 0.1 mU/L and < 0.5 mU/L:
 
 • Continue atezolizumab. • Monitor TSH every 4 weeks. 
TSH < 0.1 mU/L:
 
 • Follow guidelines for symptomatic hyperthyroidism.
Symptomatic hyperthyroidism	
 • Withhold atezolizumab. • Initiate treatment with anti-thyroid drug such as methimazole or carbimazole as needed. • Consider patient referral to endocrinologist. • Resume atezolizumab when symptoms are controlled and thyroid function is improving. • Permanently discontinue atezolizumab.

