Symptomatic adrenal insufficiency, Grade 2–4	
 • Withhold atezolizumab for up to 12 weeks after event onset.^a • Refer patient to endocrinologist. • Perform appropriate imaging. • Initiate treatment with corticosteroids equivalent to 1–2 mg/kg/day IV methylprednisolone and convert to 1–2 mg/kg/day oral prednisone or equivalent upon improvement. • If event resolves to Grade 1 or better and patient is stable on replacement therapy, resume atezolizumab.^b • If event does not resolve to Grade 1 or better or patient is not stable on replacement therapy while withholding atezolizumab, permanently discontinue atezolizumab.
Hyperglycemia, Grade 1 or 2	
 • Continue atezolizumab.

Event	Management
	
 Investigate for diabetes. If patient has Type 1 diabetes, treat as a Grade 3 event. If patient does not have Type 1 diabetes, treat as per institutional guidelines. Monitor for glucose control.
Hyperglycemia, Grade 3 or 4	
 Withhold atezolizumab. Initiate treatment with insulin. Monitor for glucose control. Consider referral to endocrinologist, particularly if patient is deemed to have atezolizumab-induced diabetes; if so, obtain C-peptide level paired with glucose, autoantibody levels (e.g. GAD65, islet cell autoantibodies), and hemoglobin A1C level. If patient is found to have diabetic ketoacidosis or hyperglycemic hyperosmolar syndrome, treat as per institutional guidelines with appropriate management and laboratory values (e.g. anion gap, ketones, blood pH, etc.) reported. Resume atezolizumab when symptoms resolve and glucose levels are stable.
Hypophysitis (pan-hypopituitarism), Grade 2 or 3	
 Withhold atezolizumab for up to 12 weeks after event onset.^a Refer patient to endocrinologist. Perform brain MRI (pituitary protocol). Initiate treatment with corticosteroids equivalent to 1–2 mg/kg/day IV methylprednisolone and convert to 1–2 mg/kg/day oral prednisone or equivalent upon improvement. Initiate hormone replacement if clinically indicated. If event resolves to Grade 1 or better, resume atezolizumab.^b If event does not resolve to Grade 1 or better while withholding atezolizumab, permanently discontinue atezolizumab. For recurrent hypophysitis, treat as a Grade 4 event.

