Grade 2 ^a Fever ^b with hypotension not requiring vasopressors and/or Hypoxia requiring low-flow oxygen ^d by nasal cannula or blow-by	
 • Immediately interrupt atezolizumab infusion. • Upon symptom resolution, wait for 30 minutes and then restart infusion at half the rate being given at the time of event onset. • If symptoms recur, discontinue infusion of this dose. • Administer symptomatic treatment.^c • For hypotension, administer IV fluid bolus as needed. • Monitor cardiopulmonary and other organ function closely (in the ICU, if appropriate). Administer IV fluids as clinically indicated and manage constitutional symptoms and organ toxicities as per institutional practice. • Rule out other inflammatory conditions that can mimic CRS (e.g., sepsis). If no improvement within 24 hours, initiate workup and assess for signs and symptoms of HLH or MAS.

	
 ● Consider IV corticosteroids (e.g., methylprednisolone 2 mg/kg/day or dexamethasone 10 mg every 6 hours). ● Consider anti-cytokine therapy.^e ● Consider hospitalization until complete resolution of symptoms. If no improvement within 24 hours, manage as per Grade 3, that is, hospitalize patient (monitoring in the ICU is recommended), permanently discontinue atezolizumab. ● If symptoms resolve to Grade 1 or better for 3 consecutive days, the next dose of atezolizumab may be administered. For subsequent infusions, consider administration of oral premedication with antihistamines, anti-pyretics, and/or analgesics and monitor closely for IRRs and/or CRS. ● If symptoms do not resolve to Grade 1 or better for 3 consecutive days, contact the Principal Investigator.

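### The symptomatic hyperthyroidism row in Section 6.2 tells sites both to resume atezolizumab and, with no condition, to stop it permanently

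*Combined protocol and SAP*

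**What the plan says.** The symptomatic hyperthyroidism row in the Section 6.2 endocrine table lists, in order: withhold the drug, start anti-thyroid treatment as needed, and consider an endocrinology referral. Its last two bullets are "Resume atezolizumab when symptoms are controlled and thyroid function is improving. • Permanently discontinue atezolizumab". The text that follows is a new row, for adrenal insufficiency, so nothing after the final bullet qualifies it.

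The row above covers asymptomatic hyperthyroidism. For TSH below 0.1 mU/L its instruction is "Follow guidelines for symptomatic hyperthyroidism", so those patients inherit whatever the symptomatic row says.

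Section 6.1 has two general stopping rules that could cover this event. One is for severity: "Atezolizumab should be permanently discontinued in patients with life threatening irAEs". The other is for long interruptions: "If atezolizumab is held because of AEs for >84 days beyond the scheduled date of infusion, the patient will be discontinued from atezolizumab". Section 6.1 also allows up to 4 weeks beyond the 84 days for tapering steroids when the event itself has resolved in time. The hyperthyroidism row refers to neither rule.

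**The concern.** The two closing bullets cannot both be followed. Once symptoms are controlled and thyroid function is improving, the first says to restart and the second says never to restart. Two sites could treat the same patient in opposite ways, and each could cite the row.

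The conflict is not confined to patients with symptoms. Sections 5 and 10 have TSH checked before each cycle, so a patient who feels well can reach this row through a routine laboratory value. Section 3.2.13 allows some patients with autoimmune hyperthyroid disease to enroll, so thyroid abnormalities are foreseeable. Sections 5.1 and 6.1 rule out dose reduction, which leaves hold, resume or stop as the only dosing choices. Section 2.1 describes no effective treatment for metastatic clear cell sarcoma, so an unintended permanent stop would be a real loss to an individual patient.

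**Working it through.** The plan gives no figure to reproduce. The check is a reading of all 50 event rows in the Section 6.2 tables, each coded for three things: an instruction to resume, an instruction to discontinue permanently, and whether the stop carries a condition.

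1. **Rows with both instructions.** There are 16: pulmonary Grade 2; hepatic Grade 2; diarrhea or colitis Grade 2 and Grade 3; symptomatic hyperthyroidism; adrenal insufficiency Grade 2–4; hypophysitis Grade 2–3; ocular Grade 2; myocarditis Grade 2; amylase/lipase Grade 3–4; pancreatitis Grade 2–3; dermatologic Grade 3; neuropathy Grade 2; renal Grade 2; myositis Grade 2 and Grade 3.

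2. **Is the stop conditional?** In 15 of the 16 it is tied to non-resolution during the hold. The usual form is "If event does not resolve to Grade 1 or better while withholding atezolizumab, permanently discontinue atezolizumab". Adrenal insufficiency adds instability on replacement therapy; the amylase/lipase and pancreatitis rows add recurrence. Symptomatic hyperthyroidism is the remaining 1 (16 − 15 = 1).

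3. **Sensitivity of the count.** The Grade 2 infusion-reaction/cytokine-release row words re-dosing differently: "If symptoms resolve to Grade 1 or better for 3 consecutive days, the next dose of atezolizumab may be administered". Its stop is also conditional. Counting it gives 16 of 17 conditional, with the same single exception.

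4. **How a site would read a bare stop bullet.** The same stand-alone sentence appears in 14 other rows, such as pulmonary Grade 3–4, colitis Grade 4 and meningoencephalitis. In those rows it is an absolute stop, and none of them has a resume bullet. A site used to these tables has grounds to read it as absolute here too.

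5. **Closest neighbors.** Two other endocrine rows withhold the drug without a 12-week limit. Symptomatic hypothyroidism closes with "Monitor TSH weekly. • Consider patient referral to endocrinologist. • Resume atezolizumab when symptoms are controlled and thyroid function is improving" and hyperglycemia Grade 3 or 4 closes with "Resume atezolizumab when symptoms resolve and glucose levels are stable". Neither has a stop bullet. Of these three open-ended rows, only hyperthyroidism carries one.

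Steps 2 and 5 point to different explanations. The 15 comparator rows suggest that a condition is missing; the two neighbors suggest that the bullet does not belong. The documents do not settle which.

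**The case against.** The strongest reply is that this may be a fault of text extraction. The bullet sits inside a table, and nearby tables have lost footnote letters. Some conditions in 6.2 stand in unbulleted sub-headings, so one could have dropped out. That possibility stands, and it is why the first step is to look at the source page. But the bullet is a complete sentence closed by a full stop, comparable sub-headings in the same table survived, and loss is not shown.

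A second reply is that sensible clinicians would not stop a controlled patient, because that would make the resume bullet pointless, and that Section 6.1 supplies a default: investigator judgment of benefit and risk plus the two general stops. Section 6.2 also points to the Investigator's Brochure for endocrinopathies. This lowers the chance of divergent treatment. It does not remove the contradiction, because the row neither cites those rules nor limits its stop to them, and the Brochure is not available here to check.

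A reader might also infer a limit on the number of patients affected by applying the 20% ceiling of the Section 7.1 band that lists hyperthyroidism to the accrual ceiling of 68 (0.20 × 68 = 13.6). The documents do not support this. The band comes from 3097 patients in other trials, is not shown to include symptom-free patients found only by a low TSH, and does not bind this trial.

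**Conclusion.** The row is wrong as written: it states a treatment rule that cannot be followed. It is the only one of 16 comparable rows with an unconditional stop (1 of 17 on the wider count). This rests on the printed text being complete; the cause, whether a lost condition or a stray bullet, is unknown.

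The consequence is limited to consistent and safe treatment of individual patients across sites. The number affected is unknown. A reader might infer that inconsistent stopping threatens the response-rate result, but nothing in the documents shows an effect on the design, sample size or analysis. Section 13.4.2 keeps eligible patients in the response analysis despite treatment deviations.

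**What to change.** Check the source page and the Investigator's Brochure for the intended wording. With the medical lead's confirmation, do one of the following.

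- **Delete the last bullet**, so that the row ends as the symptomatic hypothyroidism row does. Both Section 6.1 stops continue to apply.
- **Make the bullet conditional on Section 6.1**: permanent discontinuation for life-threatening immune-related hyperthyroidism, or when the drug has been held for more than 84 days beyond the scheduled infusion, subject to the steroid-taper extension of up to 4 weeks in that section.

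No separate line is needed for symptom-free patients with low TSH, because the existing cross-reference sends them to the corrected row. The cost is one bullet in the next amendment and a short memo to sites.

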7. ADVERSE EVENTS: LIST AND REPORTING REQUIREMENTS

Adverse event (AE) monitoring and reporting is a routine part of every clinical trial. The following list of AEs (Section 7.1) and the characteristics of an observed AE (Sections 7.2 and 7.3) will determine whether the event requires expedited reporting via the CTEP Adverse Event Reporting System (CTEP-AERS) **in addition** to routine reporting.

7.1 Comprehensive Adverse Events and Potential Risks List (CAEPR)

Comprehensive Adverse Events and Potential Risks list (CAEPR) for Atezolizumab (MPDL3280A, NSC 783608)

The Comprehensive Adverse Events and Potential Risks list (CAEPR) provides a single list of reported and/or potential adverse events (AE) associated with an agent using a uniform presentation of events by body system. In addition to the comprehensive list, a subset, the Specific Protocol Exceptions to Expedited Reporting (SPEER), appears in a separate column and is identified with bold and italicized text. This subset of AEs (SPEER) is a list of events that are protocol specific exceptions to expedited reporting to NCI (except as noted below). Refer to the 'CTEP, NCI Guidelines: Adverse Event Reporting Requirements' http://ctep.cancer.gov/protocolDevelopment/electronic_applications/docs/aeguidelines.pdf for further clarification. *Frequency is provided based on 3097 patients.* Below is the CAEPR for Atezolizumab (MPDL3280A).

NOTE: Report AEs on the SPEER **ONLY IF** they exceed the grade noted in parentheses next to the AE in the SPEER. If this CAEPR is part of a combination protocol using multiple investigational agents and has an AE listed on different SPEERs, use the lower of the grades to determine if expedited reporting is required.

Adverse Events with Possible Relationship to Atezolizumab (MPDL3280A) (CTCAE 5.0 Term) [n= 3097]			Specific Protocol Exceptions to Expedited Reporting (SPEER)
Likely (>20%)	Less Likely (<=20%)	Rare but Serious (<3%)	
BLOOD AND LYMPHATIC SYSTEM DISORDERS			
	Anemia		
CARDIAC DISORDERS			
		Heart failure (2)	
		Myocarditis	
		Pericardial effusion (2)	
		Pericardial tamponade (2)	
		Pericarditis (2)	
ENDOCRINE DISORDERS			
		Adrenal insufficiency	
		Endocrine disorders - Other (diabetes) (2)	
	Hyperthyroidism (2)		
		Hypophysitis(2)	
	Hypothyroidism (2)		
EYE DISORDERS			
		Eye disorders - Other (ocular inflammatory toxicity)(2)	
		Uveitis(2)	
GASTROINTESTINAL DISORDERS			
	Abdominal pain		Abdominal pain (Gr 2)
	Diarrhea		Diarrhea (Gr 2)
	Dysphagia		
	Nausea		Nausea (Gr 2)
		Pancreatitis (2)	
	Vomiting		Vomiting (Gr 2)
GENERAL DISORDERS AND ADMINISTRATION SITE CONDITIONS			
Fatigue			Fatigue (Gr 2)
	Fever ³		
	Flu like symptoms ³		
HEPATOBIILIARY DISORDERS			
		Hepatic failure(2)	
		Hepatobiliary disorders - Other (hepatitis) (2)	
IMMUNE SYSTEM DISORDERS			
	Allergic reaction ³		
		Anaphylaxis ³	
		Cytokine release syndrome ³	
		Immune system disorders - Other (systemic immune activation) (2)	
INFECTIONS AND INFESTATIONS			
Infection ⁴			

Adverse Events with Possible Relationship to Atezolizumab (MPDL3280A) (CTCAE 5.0 Term) [n= 3097]			Specific Protocol Exceptions to Expedited Reporting (SPEER)
Likely (>20%)	Less Likely (<=20%)	Rare but Serious (<3%)	
INJURY, POISONING AND PROCEDURAL COMPLICATIONS			
	Infusion related reaction ³		
INVESTIGATIONS			
	Alanine aminotransferase increased (2)		
	Alkaline phosphatase increased (2)		
	Aspartate aminotransferase increased (2)		
	Blood bilirubin increased (2)		
		Creatinine increased	
	GGT increased (2)		
	Lipase increased*		
	Serum amylase increased*	Platelet count decreased	
METABOLISM AND NUTRITION DISORDERS			
	Anorexia		Anorexia (Gr 2)
		Hyperglycemia (2)	
	Hypokalemia		
	Hyponatremia		
MUSCULOSKELETAL AND CONNECTIVE TISSUE DISORDERS			
	Arthralgia (2)		
	Back pain		
		Generalized muscle weakness	
	Myalgia		
		Myositis (2)	
NERVOUS SYSTEM DISORDERS			
		Ataxia (2)	
		Encephalopathy(2)	
		Nervous system disorders - Other (encephalitis non-infective) (2)	
		Guillain-Barre syndrome (2)	
		Nervous system disorders - Other (meningitis non-infective) (2)	
		Myasthenia gravis (2)	
		Paresthesia (2)	
		Peripheral motor neuropathy	
		Peripheral sensory neuropathy (2)	
RENAL AND URINARY DISORDERS			
		Acute kidney injury	

Adverse Events with Possible Relationship to Atezolizumab (MPDL3280A) (CTCAE 5.0 Term) [n= 3097]			Specific Protocol Exceptions to Expedited Reporting (SPEER)
Likely (>20%)	Less Likely (<=20%)	Rare but Serious (<3%)	
		Renal and urinary disorders - Other (nephritis) (2)	
RESPIRATORY, THORACIC AND MEDIASTINAL DISORDERS			
	Cough		Cough (Gr 2)
	Dyspnea		
	Hypoxia		
	Nasal congestion		Nasal congestion (Gr 2)
		Pleural effusion (2)	
		Pneumonitis (2)	
SKIN AND SUBCUTANEOUS TISSUE DISORDERS			
		Bullous dermatitis (2)	
		Erythema multiforme (2)	
	Pruritus		
	Rash acneiform		
	Rash maculo-papular		
		Skin and subcutaneous tissue disorders - Other (drug reaction with eosinophilia and systemic symptoms [DRESS]) (2)	
	Skin and subcutaneous tissue disorders - Other (lichen planus)		
		Skin and subcutaneous tissue disorders - Other (exanthematous pustulosis)	
		Stevens-Johnson syndrome (2)	
		Toxic epidermal necrolysis (2)	

*Denotes adverse events that are <3%.

1 This table will be updated as the toxicity profile of the agent is revised. Updates will be distributed to all Principal Investigators at the time of revision. The current version can be obtained by contacting [contact]. Your name, the name of the investigator, the protocol and the agent should be included in the e-mail.

2 Atezolizumab, being a member of a class of agents involved in the inhibition of "immune checkpoints," may result in severe and possibly fatal immune-mediated adverse events probably due to T-cell activation and proliferation. Immune-mediated adverse reactions have been reported in patients receiving atezolizumab. Adverse events potentially related to atezolizumab may be manifestations of immune-mediated adverse events. In clinical trials, most immune-mediated adverse reactions were reversible and managed with interruptions of atezolizumab, administration of corticosteroids and supportive care.

3 Infusion reactions, including high-grade hypersensitivity reactions, anaphylaxis, and cytokine release syndrome, which have been observed following administration of atezolizumab, may manifest as fever, chills, shakes, itching, rash, hypertension or hypotension, or difficulty breathing during and immediately

after administration of atezolizumab.

4 Infection includes all 75 sites of infection under the INFECTIONS AND INFESTATIONS SOC.

Adverse events reported on atezolizumab (MPDL3280A) trials, but for which there is insufficient evidence to suggest that there was a reasonable possibility that atezolizumab (MPDL3280A) caused the adverse event:

BLOOD AND LYMPHATIC SYSTEM DISORDERS - Blood and lymphatic system disorders - Other (pancytopenia); Febrile neutropenia

CARDIAC DISORDERS - Cardiac arrest; Ventricular tachycardia

GASTROINTESTINAL DISORDERS - Constipation; Dry mouth; Ileus

GENERAL DISORDERS AND ADMINISTRATION SITE CONDITIONS - Chills; Edema limbs; Malaise; Multi-organ failure

HEPATOBIILIARY DISORDERS - Portal vein thrombosis

INVESTIGATIONS - Lymphocyte count decreased; Neutrophil count decreased; Weight loss; White blood cell decreased

METABOLISM AND NUTRITION DISORDERS - Hypophosphatemia; Tumor lysis syndrome

MUSCULOSKELETAL AND CONNECTIVE TISSUE DISORDERS - Bone pain; Muscle cramp; Pain in extremity

NERVOUS SYSTEM DISORDERS - Headache

PSYCHIATRIC DISORDERS - Confusion; Insomnia; Suicide attempt

REPRODUCTIVE SYSTEM AND BREAST DISORDERS - Breast pain

RESPIRATORY, THORACIC AND MEDIASTINAL DISORDERS - Bronchopulmonary hemorrhage; Pulmonary hypertension; Respiratory failure

SKIN AND SUBCUTANEOUS TISSUE DISORDERS - Alopecia; Dry skin²; Hyperhidrosis

VASCULAR DISORDERS - Hypertension; Hypotension; Thromboembolic event

Note: Atezolizumab (MPDL3280A) in combination with other agents could cause an exacerbation of any adverse event currently known to be caused by the other agent, or the combination may result in events never previously associated with either agent.

